Subjects will be randomized to active Naltrexone 25mg, Naltrexone 50mg, and placebo groups in a 1:1:1 ratio using a computer randomization procedure at the CMHC research pharmacy, blind to both research team and subjects. Separate randomization schedules will be applied based on gender, and antipsychotic agent to yield an equal number of male and female subjects in each arm. This is to control for possible differential gender and racial/ethnicity specific effects of Naltrexone on weight as well as differences brought on by higher and lower weight liability medications.

Subjects will take the study medication daily for 52 weeks. Subjects will be seen weekly for the first 4 weeks of the study, thereafter they will be seen on a bi-weekly (every other week) basis to be assessed (i.e. weight, side effect check, paper questionnaires) throughout the remaining 48 weeks of treatment. Compliance will be monitored by pill counts as well as 25mg riboflavin added to the capsules which provides florescence to urine under Wood's lamp (UV or black light). Subjects will be given a study identification card listing the fact that they may be taking naltrexone and this card will include the study emergency cell phone number which will be available 24 hours a day, 7 days per week in case of an emergency.

The study is planned to be run at the Connecticut Mental Health Center (CMHC) and its affiliated satellite clinics throughout the greater New Haven area.

All participants will be carefully assessed with physical examination and laboratory findings, any medical problems that need immediate attention will be referred to each participant's own primary care physician. All potential subjects will meet with study staff for intake and evaluation sessions to determine eligibility prior to enrollment.

A description of assessments is given below:

1) Intake interview including demographics, clinical history, Structured Clinical Interview for DSM-IV (**SCID**) to ascertain diagnosis. 2) Urine toxicology (**Utox**) screen to rule out substance use. The initial sample will also be sent to the lab to confirm opiate results for safety purposes and a follow-up sample will be taken immediately before randomization to study medication to ensure it is negative for opiates; continued random testing will occur at the discretion of the study physician throughout the trial along

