
4. Genetic Testing N/A

A. Describe

- i. the types of future research to be conducted using the materials, specifying if immortalization of cell lines, whole exome or genome sequencing, genome wide association studies, or animal studies are planned
- ii. the plan for the collection of material or the conditions under which material will be received

Assessment Schedule

SCID, Demographics, Physical exam	Week 0
Urine toxicology, pregnancy test for female subjects	Week 0 and every 4 weeks subsequently + as needed
Fluorescence check in urine for compliance	determined by study physician
Fasting Glucose, Insulin, HbA1c, Lipid Profile, Liver function tests	Week 0, 16, 32, 52
Serum leptin, ghrelin, peptide YY, adiponectin, high sensitivity	Week 0, 16, 52
CRP, interleukin 6	
Framingham Score	Calculated same time with blood draws.
Vitals (Blood Pressure, pulse)	Weekly for first 4 weeks, then every two weeks
Weight, BMI	Weekly for first 4 weeks, then every two weeks
RMR, Waist Circumference (WC), 24hr Food Recall, TFEQ, YPAS, BPRS, BDI, QCSRF, QLS, SF-36, C-SSRS.	Week 0 and every 4 weeks
UKU side effects	Weekly for first 4 weeks, then every two weeks
Cognitive Battery	Week 0, Week 16, Week 52

- iii. the types of information about the donor/individual contributors that will be entered into a database
- iv. the methods to uphold confidentiality

- B. What are the conditions or procedures for sharing of materials and/or distributing for future research projects?
- C. Is widespread sharing of materials planned?
- D. When and under what conditions will materials be stripped of all identifiers?
- E. Can donor-subjects withdraw their materials at any time, and/or withdraw the identifiers that connect them to their materials?
 - i. How will requests to withdraw materials be handled (e.g., material no longer identified: that is, anonymized) or material destroyed)?
- F. Describe the provisions for protection of participant privacy
- G. Describe the methods for the security of storage and sharing of materials

5. Subject Population: Provide a detailed description of the types of human subjects who will be recruited into this study.

200 patients with severe mental illness

6. Subject classification: Check off all classifications of subjects that will be specifically recruited for enrollment in the research project. Will subjects who may require additional

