- 4) On a stable dose of antipsychotic medication; i.e. at least one month with no dose change, and three months from an antipsychotic switch
- 5) Deemed to be symptomatically stable by the clinical staff in the last two months

6) Over 7% total body weight increase on antipsychotics for subjects within first year of illness

Exclusion Criteria

- 1) Meet criteria for current opiate abuse or dependence (confirmed by positive urine drug screen for opiates or, if suspected by study doctor via patient history and or suspicion of occult opiate use, a naloxone challenge will be performed.)
- 2) Current history of dementia, mental retardation
- 3) Not capable of giving informed consent for participation in the study
- 4) Women who are pregnant or breast-feeding
- 5) Physical conditions affecting body weight (e.g. Cushing's disease, polycystic ovary syndrome)
- 6) Diabetes Mellitus (defined as prescribed an anti-diabetic medication for diabetes or a hemoglobin A1c level > 7 confirmed by primary care physician at screening)
- 7) Severe liver dysfunction, (serum aminotransferases greater than three times normal), acute infectious hepatitis, liver failure.

8. How will **eligibility** be determined, and by whom?

Eligibility will be determined through participant report, chart review, and communication with CMHC clinician/psychiatrist, and this will be completed by the PI and research coordinator.

9. **Risks:** Describe the reasonably foreseeable risks, including risks to subject privacy, discomforts, or inconveniences associated with subjects participating in the research.

Naltrexone 25mg/50mg/Placebo

Hepatotoxicity: Liver functions reported to be effected in terms of increased liver transaminase levels at doses of naltrexone 10 to 12 times the study dose. No hepatotoxicity reported at or twice the study dose.

Opioid Withdrawal: Naltrexone may cause acute withdrawal on subjects who had used opioids as far as seven days before the drug administration. Symptoms commonly associated with opiate withdrawal include severe nausea, abdominal cramping, diarrhea, vomiting, muscle aches, anxiety, and sweating.

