Reduced efficacy of opioid medications with naltrexone: Patients taking naltrexone may not benefit from opioid containing medicines, such as cough and cold preparations, antidiarrheal preparations, and opioid analgesics. In an emergency situation when opioid analgesia must be administered to a patient taking naltrexone, the amount of opioid required may be greater than usual, and the resulting respiratory depression may be deeper and more prolonged. Study participants will carry an information card to be used in case of an emergency.

Small increased risk of depression, suicidal ideation, and suicide: Based on data from placebo controlled trials in patients with alcohol and/or opiate dependence there was observed an infrequent however small increased incidence of depression, suicidal ideation, attempts, and completed suicides in the naltrexone treated group compared to the placebo group.

Other Side Effects: In an open label safety study with approximately 570 individuals with alcoholism receiving naltrexone, the following new-onset adverse reactions occurred in 2% or more of the patients: nausea (10%), headache (7%), dizziness (4%), nervousness (4%), fatigue (4%), insomnia (3%), vomiting (3%), anxiety (2%) and somnolence (2%).

Exposure to Naltrexone during Pregnancy: Naltrexone is a pregnancy Category C medication meaning the drug should be given to patients only if the potential benefit justifies the potential risk to the fetus. There is no data on the use of naltrexone or other opioid antagonists in pregnant women. The effects, if any, on the developing fetus are unknown. We will require that female patients of child bearing age use contraception to prevent pregnancy during participation in the study and will not enroll participants who are pregnant or who are trying to get pregnant.

Urine collection

Urine specimens are collected for research assessments and should pose no appreciable risks, and will be done using established procedures already in place at CMHC.

Blood collection

Subjects participating in these studies will have multiple blood draws using established procedures in the CMHC. The blood draw has the risk of producing a bruise at the venipuncture site, and rarely development of a small infection.

Cognitive Assessments, Rating Scales and Questionnaires

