- The drug is intended solely for tests in vitro or in laboratory research animals if shipped in accordance with 21 CFR 312.60

Exempt Category 4

- A clinical investigation involving use of a placebo if the investigation does not otherwise require submission of an IND.

2. **Background Information:** Provide a description of previous human use, known risks, and data addressing dosage(s), interval(s), route(s) of administration, and any other factors that might influence risks. If this is the first time this drug is being administered to humans, include relevant data on animal models.

Pharmacodynamic Actions: Naltrexone is a pure opioid antagonist. It markedly attenuates or completely blocks, reversibly, the subjective effects of intravenously administered opioids. When co-administered with morphine, on a chronic basis, naltrexone blocks the physical dependence to morphine, heroin and other opioids. Naltrexone has few, if any, intrinsic actions besides its opioid blocking properties. However, it does produce some pupillary constriction, by an unknown mechanism.

The administration of naltrexone is not associated with the development of tolerance or dependence. In subjects physically dependent on opioids, naltrexone will precipitate withdrawal symptomatology. Clinical studies indicate that 50 mg of naltrexone hydrochloride will block the pharmacologic effects of 25 mg of intravenously administered heroin for periods as long as 24 hours. Other data suggest that doubling the dose of naltrexone hydrochloride provides blockade for 48 hours, and tripling the dose of naltrexone hydrochloride provides blockade for about 72 hours.

Naltrexone blocks the effects of opioids by competitive binding (i.e., analogous to competitive inhibition of enzymes) at opioid receptors. This makes the blockade produced potentially surmountable, but overcoming full naltrexone blockade by administration of very high doses of opiates has resulted in excessive symptoms of histamine release in experimental subjects.

The mechanism of action of naltrexone in alcoholism is not understood; however, involvement of the endogenous opioid system is suggested by preclinical data. Naltrexone, an opioid receptor antagonist, competitively binds to such receptors and may block the effects of endogenous opioids. Opioid antagonists have been shown to reduce alcohol consumption by animals, and naltrexone has been shown to reduce alcohol consumption in clinical studies.

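### The protocol names a seven-day opioid withdrawal window, but no entry criterion requires seven opioid-free days before the first capsule (minor safety improvement)

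*Combined protocol and SAP*

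**What the plan says.** **The risk.** Section V, item 9 (Risks, Opioid Withdrawal) states: "Naltrexone may cause acute withdrawal on subjects who had used opioids as far as seven days before the drug administration". That paragraph lists the symptoms but gives no preventive step. Item 10 (Minimizing Risks) only refers back to it.

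**Entry.** Exclusion 1 (Section V, item 7) removes people with current opiate abuse or dependence. It calls for a naloxone challenge only if the study doctor has grounds for suspicion. Under item 3 (Research Plan, assessment 2) the first urine result is confirmed by the laboratory, and then "a follow-up sample will be taken immediately before randomization to study medication to ensure it is negative for opiates". Item 8 bases eligibility on what the participant reports, the chart and contact with the treating clinician. The contraindications in Section VI, A.2 include taking opioid analgesics, current dependence, acute withdrawal, and a failed challenge or positive screen.

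**During treatment.** Urine toxicology is scheduled at "Week 0 and every 4 weeks subsequently + as needed", and "continued random testing will occur at the discretion of the study physician throughout the trial". Item 11 of the consent quiz (Section V, item 6) has subjects affirm that taking study medication alongside an opiate may cause withdrawal.

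**Who is at risk.** Section VI, A.2 (Pharmacodynamic Actions) adds: "In subjects physically dependent on opioids, naltrexone will precipitate withdrawal symptomatology".

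**The concern.** The protocol identifies an interval within which a first dose may precipitate withdrawal, and then does not use that interval to decide who may be dosed. Its entry checks ask whether someone is using, dependent or testing positive now. None asks when an opioid was last taken. Recent prescribed use that has ended is the case most likely to slip between them.

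At stake is an acute, avoidable reaction (severe nausea, vomiting, cramping) on starting study medication. It can occur only in the two naltrexone arms. Because staff and subjects are blinded, any safeguard has to be written for all three arms. The efficacy analysis is not affected.

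**Working it through.** There is no planned figure to reproduce. The check sets each entry safeguard beside the seven-day window.

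| Safeguard | Where | What it tests | Opioid-free period stated? |
|---|---|---|---|
| Exclusion 1 | Section V, item 7 | Current abuse or dependence | No |
| Naloxone challenge | Section V, item 7 | Response to naloxone, only on suspicion | No |
| Laboratory-confirmed first urine | Section V, item 3 | Opiates in that sample | No |
| Repeat urine before randomisation | Section V, item 3 | Opiates in that sample | No |
| Report, chart, clinician contact | Section V, item 8 | General eligibility | No |
| Contraindications 1 to 4 | Section VI, A.2 | Present analgesic use, present dependence, acute withdrawal, failed challenge or positive screen | No |

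**A worked case.** Take a subject whose prescribed opioid course ended 3 days before the first capsule (an illustrative figure). The subject is not judged dependent, is not in withdrawal and has negative urine.

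1. Since 3 is less than 7, the subject is inside the stated risk window.
2. Exclusion 1 does not apply, because there is no current abuse or dependence.
3. No challenge is triggered unless the study doctor is suspicious.
4. Both urine requirements are met. The documents give neither a detection window nor the range of opioids detected, so a negative result cannot be converted into a number of opioid-free days.
5. No contraindication applies, because each describes a present state or a test result.

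The subject meets every written entry criterion. A seven-day rule would move the first capsule by 7 − 3 = 4 days. For last use *d* days earlier the delay is 7 − *d*, so never more than a week.

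**Number exposed.** Under 1:1:1 allocation of 200 subjects, 200 × 2/3 ≈ 133 receive naltrexone. That is the number exposed to the drug, not the number at risk. The documents give no rate of recent opioid use, so the number at risk cannot be derived.

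**Restart during the 52 weeks.** The supplied text has no rule on how long to wait before resuming capsules after opioid use. Two statements limit what follows from this. With chronic co-administration, "naltrexone blocks the physical dependence to morphine, heroin and other opioids", so the remaining case is opioid use while capsules are interrupted. For a subject who has become dependent, contraindication 2 already forbids dosing. What is missing there is an interval to apply, not a prohibition.

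**The case against.** **Entry is already well guarded.** There are two urine checks, one of them immediately before randomisation, plus chart review, clinician contact and a challenge on suspicion. Baseline spans three appointments (Section X, item 2), which gives several chances to learn of opioid use. Precipitated withdrawal is tied to physical dependence, and dependent subjects are named in exclusion 1 and contraindication 2. Most of this stands, and it is why the point is minor. It does not close the gap: recognising dependence relies on history or suspicion, and nothing requires the date of last use to be asked.

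**Restart.** A reader might infer that a subject could use opioids during an interruption and resume at home without contravening anything in the plan. The documents do not support that. Contraindications 2 and 3 cover a subject who is dependent or in withdrawal, and quiz item 11 warns of the consequence. The quiz is an imperfect safeguard. If its 11 items count equally, the 80% pass mark needs 0.80 × 11 = 8.8, so 9 correct, and item 11 can be missed; it also states no interval. But a home restart depends mainly on instructions to the subject, which may sit in the removed consent pages or the opiate list to which the quiz refers.

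Nor does the item 9 text on emergencies "when opioid analgesia must be administered to a patient taking naltrexone" establish the restart case, because it concerns someone still taking the drug.

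**Sizing.** It is tempting to compare the 14-day visit and 28-day urine spacing with the seven-day window, or to count days since blockade lapsed from the statement that "50 mg of naltrexone hydrochloride will block the pharmacologic effects of 25 mg of intravenously administered heroin for periods as long as 24 hours". Those are facts about the calendar and about heroin effects. They are not probabilities of withdrawal, and no document says that dependence develops within such a gap.

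**Conclusion.** The point holds for entry. The protocol states a seven-day risk window and has no criterion that enforces it, so a recently treated subject with negative urine can be started inside the window under the plan as written.

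The conclusion assumes that the first capsule follows soon after randomisation, since no interval between them is stated, and that a negative urine does not by itself guarantee seven opioid-free days, since no look-back is given. The gap cannot be sized. Existing checks narrow it, and the risk is mainly to physically dependent users whose dependence goes unrecognised.

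For restarts the finding is smaller: an interval is absent from the supplied text, but part of the protection is already there. Overall this is a minor safety improvement, worth making because it is cheap.

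**What to change.** 1. In Section V, item 7, add an exclusion for opioid use in the seven days before the first capsule. State that randomisation is delayed, not refused. Where the study doctor is in doubt, allow a negative naloxone challenge, which exclusion 1 already uses, as the alternative.
2. In Section V, item 3, record the date of last opioid use beside the pre-randomisation urine sample.
3. As a minor addition, state in the dosing text that after opioid use during an interruption capsules are resumed only after the same interval or a negative challenge. Check that any instructions to subjects in the consent form agree.

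The cost is wording in three places and one dated question at visits already planned. The downside is that some starts or restarts are delayed, including for non-dependent users at low risk, such as someone who took an opioid-containing cough or antidiarrhoeal medicine. At entry the delay is at most seven days. How many subjects would be delayed cannot be estimated from the documents.

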first episode patients is similar to population controls during initial assessment¹⁵. On the other hand, after one year of treatment, mean BMI increased by 9% in first episode schizophrenia patients (n=79) vs. 1% in age matched population controls (N=156). During this period, Framingham 10 year CV risk score disproportionately and significantly increased from 0.7 to 1.22 for first episode patients, whereas it remained similar (0.74 to 0.79) in population controls. Both results were highly significant (manuscript in preparation). These findings from our group provide preliminary evidence that obesity is not a direct result of schizophrenia. Indeed, several lines of evidence support this notion. First, pre-antipsychotic era historical data typically points to lower than population average body weight, even after the development of specialized nutrition programs to bring patients up to population weight norms^{16,17}. Second, historical data also suggest normal fasting sugar and oral glucose tolerance tests among schizophrenia patients¹⁸. Third, untreated chronic schizophrenia patients, as can be found and studied in India, appear to have lower body weight and metabolic profiles that are similar to those of historical cohorts¹⁹. Fourth, first reports of excessive increases in body weight initially appeared following the introduction of first-generation antipsychotic medications^{20,21}. Combined with the short and long term weight gain observed with antipsychotic use in various patient groups, the evidence indicates that increased obesity in schizophrenia is largely an iatrogenic problem²². In ours and other's analyses of risk factors for obesity, it is clear that obesity rates are closely associated with the appetite-increasing side effects of antipsychotic medications²³. Patients on antipsychotic medications consume more total fat and sugar than comparable populations (in press)²³. They also perform significantly less moderate physical activity, and have less nutritional knowledge than matched general population samples (in press).

Antipsychotics significantly contribute to the increased rates of obesity, and related medical

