Data will be electronically scanned into databases and will be double checked by hand. Hard copy documents will be examined to verify questionable observations. Missing data will be examined for each variable. Histograms, normal probability plots, and numerical summaries (skewness, kurtosis) will be used to examine distributional assumptions required for the mixed model analysis described below. Transformations such as the logarithm, square root, and reciprocal will be considered in the event the normality assumption is inadequate. Residual analysis will also be performed to evaluate distributional variance and linearity assumptions. Data analysis will be conducted in collaboration with [name], statistician in the department of Psychiatry and [name] faculty member of the Department of Biostatistics at Yale University School of Public Health. For all analyses, an alpha threshold of 5% (two-sided) will be used to test for statistical significance and will be performed using SAS v9.3 (SAS Institute, Cary, NC).

Analyses will be performed according to the intent-to-treat (ITT) principle where data from any randomized subjects will be analyzed. We will calculate descriptive statistics for participants at baseline, and compare naltrexone to placebo participants using analysis of variance (ANOVA) for normally distributed covariates and chi-square tests for categorical covariates. The impact of baseline variables that demonstrate clinically relevant group differences will be assessed in supportive analyses using covariate adjustment.

Approach to Missing Data: The primary analysis method will use a likelihood-based mixed model, which accommodates incomplete observations and operates under the assumption that the missing data is missing at random (MAR). Missing data patterns, time to withdrawal and reasons for dropout will be compared between the two naltrexone and placebo groups. T-tests, cross-tabulations, and logistic regression will be used to evaluate whether withdrawal is dependent on any observed variables. Finally, should missing data patterns and reasons for missing data suggest a bias or confounding, we will conduct sensitivity analyses using pattern mixture models to examine the influence that dropout bias (informative missingness) may have on treatment differences. Multiple imputation (MI) will also be used in the case of data not MAR. Sensitivity analyses will be performed secondarily among study completers.

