Hypothesis Testing: The primary goal of this study is to compare the weight changes resulting from two different doses of naltrexone compared to placebo. The primary ITT analysis will employ a linear mixed effects model (LMM) to determine the effect of treatment status (between-subjects for: naltrexone 25/50mg vs. placebo) on the trajectory of weight change over time (within-subjects for: study time points). The interaction between treatment and time will be modeled and interpreted using graphical displays and post-hoc contrasts on least square means. The latter will include estimation of group contrasts at each time point and polynomial (linear, etc.) contrasts for time within each group. However, the primary contrasts will be each dose compared with control at 52 weeks. Because the outcome data are correlated (i.e., weight assessed from the same subject at different time points), weight over time will be modeled through the inclusion of random subject effects and/or structured variance-covariance matrices, with the best-fitting structure determined by Bayesian-Schwartz Information criteria (BIC). Supportive analyses will also include covariate adjustment for clinically significant variables (as determined from baseline evaluations and also other treatment variables, such as sessions attended). The above model will be fit using SAS PROC MIXED (Cary, NC), using restricted maximum likelihood (REML). The effect of treatment assignment on the secondary outcomes, such as BMI, waist circumference, serum lipid profile, fasting glucose, and glycosylated hemoglobin (HbA1c) will be evaluated using the linear mixed modeling approach described above. The proportion of subjects achieving 3, 4, or 5% weight loss will be compared between the treatment groups with the Fisher's Exact test. Type 1 error for secondary outcomes will be adjusted using the Bonferroni correction, basing the adjustment on the number of conceptually related statistical tests.

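### Baseline covariates for the supportive models are picked from group differences seen after randomisation, so prognostic value plays no part and the stratification factors are the least likely to be chosen

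*Combined protocol and SAP*

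**What the plan says.** Section V, item 12 (Statistical Considerations) plans to "compare naltrexone to placebo participants using analysis of variance (ANOVA) for normally distributed covariates and chi-square tests for categorical covariates". The next sentence gives the rule for using the result: "The impact of baseline variables that demonstrate clinically relevant group differences will be assessed in supportive analyses using covariate adjustment". The Hypothesis Testing paragraph of the same item says that supportive analyses will include "covariate adjustment for clinically significant variables (as determined from baseline evaluations and also other treatment variables, such as sessions attended").

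Neither place lists a baseline variable, sets a size of difference that triggers adjustment, or asks whether a variable predicts weight change. The primary model is described through treatment, time and their interaction, with each dose compared with placebo at week 52. No baseline covariate is named for it.

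Section V, item 3 (Research Plan) randomises subjects to the two dose groups and "placebo groups in a 1:1:1 ratio using a computer randomization procedure", with separate schedules by gender and antipsychotic agent. The reason given is that naltrexone's effect on weight may differ by gender and that antipsychotics differ in weight liability. Neither factor is named as a model term in item 12.

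**The concern.** Under proper randomisation every baseline difference between arms is a chance event. A significance test of such a difference examines a null hypothesis already known to be true. A rule that adjusts for whatever differs therefore selects at random with respect to the property that makes adjustment useful, which is the variable's relation to weight change.

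The rule also works against the protocol's own reasoning. Gender and antipsychotic agent were judged important enough to stratify. Stratification balances them, so they are the variables least likely to show a difference and least likely to be adjusted for.

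What is at stake is the value of the supportive analyses. Without a list or a threshold, their terms are settled after the arms have been compared. They will usually leave out useful predictors, and a chance difference in an unimportant variable can bring that variable in.

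**Working it through.** The documents give no power calculation and no figure on this point, so there is nothing of the plan's own to reproduce. The check asks how often the rule would select a given variable, and what that does to precision.

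**Inputs from the documents.** N is 200 (Section V, item 5: "200 patients with severe mental illness"), allocated 1:1:1, so about 67/67/66. Item 12 sets the level: "For all analyses, an alpha threshold of 5% (two-sided) will be used to test for statistical significance".

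**Assumptions not in the documents.** Standardised effect d = 0.5; correlation r between covariate and outcome of 0.2 to 0.5; no dropout; and the trigger for adjustment, since the plan's wording has no numerical meaning.

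**1. Chance that one variable is left out.** With a 5% test, a randomised variable is flagged 5% of the time and left out 95% of the time, however strong a predictor it is. If the trigger is instead a standardised mean difference above t, 200,000 simulated draws at 67/67/66 give:

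| t | left out, any pair of arms | left out, pooled naltrexone v placebo |
|---|---|---|
| 0.1 | 17% | 49% |
| 0.2 | 52% | 82% |
| 0.25 | 68% | 90% |
| 0.3 | 81% | 95% |
| 0.5 | 99% | over 99% |

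The pooled column can be checked by formula. The standard error is √(1/134 + 1/66) = 0.150. At t = 0.2, z = 0.2/0.150 = 1.33, so the variable is flagged 18% of the time and left out 82%. These figures are for unstratified variables; stratified factors would be flagged less often.

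**2. Chance that something is flagged.** For k independent variables tested at 5%, this is 1 − 0.95^k: 40% for k = 10 and 64% for k = 20.

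**3. Power for one dose v placebo, 66 per arm.** The noncentrality is [d/√(1 − r²)] × √(n/2), with √(66/2) = 5.745.

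- Unadjusted: 0.5 × 5.745 = 2.87, power 81%.
- Covariate fixed in advance, r = 0.2: 2.93, power 83%.
- r = 0.3: 3.01, power 85%.
- r = 0.4: 3.13, power 88%.

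Simulating the rule with selection at baseline p < 0.05 and r = 0.4 gives about 82%. That is within a point of no adjustment, so the rule recovers little of the available gain.

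**4. Size of the test.** With no treatment effect, the same simulated rule rejects about 4.5% to 4.7% of the time at r = 0.4 and 4.2% to 4.4% at r = 0.5, depending on the run. It is slightly conservative, not inflated.

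**The case against.** The strongest reply is that the rule is confined to supportive analyses, which are there to see whether an observed imbalance moves the result. They were not given the job of gaining precision. The confinement is real and it limits the point. A reader might infer that the primary week-52 test loses power, or that the trial would need 19% more subjects (1/(1 − 0.16) − 1 at r = 0.4). The documents do not support that, because the rule does not choose the primary model's terms. What remains is that a robustness check is weak when its content is settled by the observed arm differences under an undefined criterion.

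A second reply is that the plan speaks of clinical relevance, not of p < 0.05. That is correct, and the 5% trigger above is an assumption. The result holds for standardised differences of 0.2 or more and fails at 0.1. The Hypothesis Testing wording might also be read as allowing choice on clinical grounds, but it is tied to the baseline evaluations and names no baseline variable. The additional mention of sessions attended brings in a post-randomisation variable and supplies no prognostic baseline covariate.

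Third, the gain depends on r, which the documents do not give. At r = 0.2 it is about 1 to 2 points. The pilot found baseline weight uncorrelated with weight change, and diabetes, the confounder reported from the pilot, is an exclusion here.

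Three stronger readings should be set aside.

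- A reader might take the Background's report that "mean BMI increased by 9% in first episode schizophrenia patients (n=79") over one year as proof that first-year status is a strong predictor in this trial. That comparison is with population controls, not with later-stage patients. Trial entrants in their first year of illness must already have gained over 7% of body weight. If 5%, 10% or 20% of subjects were in their first year (an assumption), r = 0.4 would need a gap in weight change of 0.4/√(p(1 − p)), about 1.8, 1.3 or 1.0 SD. First-year status is a candidate only.
- A reader might infer that the baseline wording pools the two doses and hides an imbalance in one of them. ANOVA suits three groups, and the plan also uses naltrexone v placebo as shorthand where each dose is contrasted separately.
- A reader might infer a raised false-positive rate. The simulated error goes the other way.

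**Conclusion.** The point holds for the supportive analyses. The stated rule selects baseline covariates by chance difference and passes over the factors that the protocol itself treats as relevant to weight. Under a 5% trigger any given variable is omitted 95% of the time; under thresholds of 0.2 or more it is omitted in 52% or more of trials. With 66 per arm and d = 0.5, the precision forgone in those models corresponds to about 1 to 6 points of power for r from 0.2 to 0.4. The effect, correlation, trigger and absence of dropout are all assumptions. The primary contrasts are not chosen by this rule, and there is no inflation of type I error. This is a worthwhile and inexpensive correction, not a threat to the main result.

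**What to change.** In Section V, item 12:

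1. Replace the baseline ANOVA and chi-square tests with descriptive baseline tables for the three arms.
2. Before unblinding, fix the adjustment set for the supportive models on prognostic grounds. It should contain at least gender and antipsychotic agent (or weight-liability class), because these were used to randomise. Add other intake variables judged prognostic, for example age and diagnosis, with first-year status considered as a candidate.
3. Use that set whatever balance is observed.
4. Label any further model prompted by an observed imbalance as exploratory.

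The cost is SAP wording and a few degrees of freedom. No new data are needed: the stratification factors are known at randomisation, demographics, clinical history and diagnosis are collected at intake, and first-year status is needed to apply inclusion criterion 6.
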